All participants will be screened for their willingness/ability to participate in the various study procedures (see Appendix for MRI screening questionnaire) and those unwilling/unable to participate in a specific procedure will be excluded from that study. Prior to enrollment onto the study, potential research subjects will be sent a Study Questionnaire form to assist the research team in confirming diagnosis and determining which tests will be appropriate for the subject (see appendix E). The questionnaire will also guide medical record gathering prior to the visit to aid consultants. The initial screening visit will consist of laboratory evaluation initial laboratory assays in addition to a focused clinical exam and history. The objectives of the screening visit are a) exclude any contraindication for CCTA, nitrates or beta blockers (e.g. history of hyperthyroidism, aortic stenosis or prior use of sildenafil); b) determine lipid levels and c) determine if noncalcified plaque is present. Study subjects already receiving high intensity therapy for more than 90 days prior to enrollment will not be considered. Study subjects will be eligible for at least moderate statin therapy according to ACC/AHA 2013GRCR criterion and 2018 ACC/AHA guidelines. Note that study subjects at low GCRC cardiovascular risk (using traditional risk factors) but with CAC score > 75th percentile for age, gender and ethnicity will be classified to be moderate risk. Specific inclusion/exclusion criteria are indicated in Sections 2.1 and 2.2 below.

If a) noncalcified coronary plaque is identified on CCTA, and b) the study subject qualifies for at least moderate statin therapy, the study subject will be enrolled for statin therapy and follow-up. Only study subjects with a noncalcified plaque component extending over 4 mm will be considered for further follow-up in the study.

IMAGING - OVERVIEW

Imaging consists of CCTA for plaque evaluation at baseline, 12 months 24 months, and 36 months. Cardiac MRI may be performed at baseline, and 24 months (optional). A clinical report of imaging and lab results will be offered to all subjects and – if requested by the subject – can be sent to a physician.

A study of F18 NaF PET imaging will be conducted; participation in the PET study will be considered to be optional for participants. Lack of participation will not exclude subjects from the study cohort.

CT IMAGING

CT Imaging protocol

1. Coronary calcium scan

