- 4) **Secondary analysis of the above patients:** In addition to the ITT and missing data approaches mentioned in 1)-3), our secondary analysis of the primary endpoint (change of plaque volume between baseline and 36 months) will also include: a) non-ITT approach of including only treatment compliant patients in the analysis, b) complete data approach of using only patients with observed plaque volumes in both baseline and 36 months. As a sensitivity analysis, we will compare the results obtained from a) and b) above with the primary analysis of 1)-3). This sensitivity analysis will provide useful insights into the characteristics of the patients with noncompliance and/or missing plaque volume data at 24 and 36 months.

Secondary Analysis with Subgroups and Covariates: Regression models will be considered for the analysis of secondary endpoints.

- 1) **Cross-Sectional Data:** Regression models with cross-sectional outcome and covariates, i.e. data without repeated measurements over time, will include multivariable linear and nonlinear models. Nonparametric smoothing methods, such as splines and local polynomials, will be used to explore the relationships between the outcome and covariates. The flexible ANOVA F Goodness-of-Fit tests will be used to test the adequacy of the parametric linear and nonlinear regression models.
- 2) **Longitudinal Outcome and Covariate Data:** For data including repeatedly measured outcome and/or covariates over time, we will consider the commonly used linear and nonlinear mixed effects models to explore the time trends of the outcome variables and corresponding covariate effects. Similar to the exploratory analysis with cross-sectional data, we will also consider the flexible nonparametric longitudinal regression methods, such as the time-varying coefficient models and models of functional data analysis, to evaluate the appropriateness of the parametric mixed effects models.

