- 3) **For Secondary endpoint 3 (relationship of CCTA plaque to T1 CMR signal):** CMR high signal intensity plaque is postulated to represent “unstable” plaque or plaque containing hemorrhage and/ or protein. CCTA plaque characteristics that are thought to be associated with unstable plaque include spotty calcification and low density plaque. Since this aim represents an exploratory aim with the use of technologically advanced CMR imaging, the incidence of CMR T1 high signal intensity plaque is unknown. We will therefore use descriptive statistics to relate the presence or absence of T1 high signal intensity to the presence or absence of various CCTA plaque characteristics. In addition, we will determine if T1 signal changes in various plaques over the study period; if T1 signal changes (e.g. due to plaque healing), we would expect that this would be more common in the presence of unstable plaque features by CCTA. For this aim, the number of T1 high signal intensity plaques at baseline that do not show high signal at 24 months will be determined. The percentage of these plaques that demonstrated unstable CCTA plaque characteristics at baseline will be determined. Data for both the 12 and 24 month time points will be considered because at present the time course of change of high T1 signal intensity plaques is not known
- 4) **For Secondary endpoint 4 (pilot study, relationship of CCTA plaque to F18-NaF signal):** A comparison of the presence or absence of NaF signal by PET will be performed. NaF signal (with both TBR and SUVmax) will be compared across different plaque morphology and compositions defined by CCTA (for example, presence of a lipid core or calcification) in order to gain an understanding of the relationships between these two imaging modalities. Correlation between imaging findings and changes will be made with age, gender, traditional risk factors (height,

weight, hypertension, etc.), absolute values and changes in statin dose, total cholesterol, LDL, HDL, triglycerides and hematological biomarkers markers of inflammation, thrombosis and atheroprotection.

Safety Monitoring of Adverse Events: Because the statin treatment is known to be safe and involve minimal risk, we do not plan a statistical stopping rule. Any adverse events will be reported to the DSMB. Continuation or stopping of the study because of the safety reasons will be made following the recommendations of the DSMB.

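### Secondary endpoint 3: the unstable share among plaques that lose T1 signal does not, by itself, show whether signal loss is more common in unstable plaques

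*Combined protocol and SAP*

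**What the plan says.** The method is in Section 6, Secondary Analysis with Subgroups and Covariates, item 3.

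- **Expectation.** If T1 signal changes, "we would expect that this would be more common in the presence of unstable plaque features by CCTA".
- **Change analysis.** Two quantities are specified. First, "the number of T1 high signal intensity plaques at baseline that do not show high signal at 24 months will be determined". Second, "The percentage of these plaques that demonstrated unstable CCTA plaque characteristics at baseline will be determined".
- **Presence analysis.** The same item will "use descriptive statistics to relate the presence or absence of T1 high signal intensity to the presence or absence of various CCTA plaque characteristics". This concerns whether T1 signal is present, not whether it changes.
- **Status.** The item calls the aim exploratory and gives as a reason that "the incidence of CMR T1 high signal intensity plaque is unknown". The list of secondary endpoints in Section 1 labels it a pilot study.
- **General modelling statement.** The subsection opens with "Regression models will be considered for the analysis of secondary endpoints". No model of T1 signal loss on CCTA features is named.
- **Availability of CMR.** The imaging overview in Section 1 makes CMR optional, at baseline and 24 months only. Section 7.1 adds that participants in the reproducibility sub-study do not have it.

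**The concern.** The expectation compares two rates: the proportion of unstable plaques that lose signal, and the proportion of other plaques that lose signal. The stated percentage looks only at plaques that lost signal and asks how many had been unstable. It sets nothing beside that figure, neither the unstable share among plaques that kept their signal nor the loss rate in plaques without unstable features.

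The figure therefore depends heavily on how common unstable features are among T1-high plaques in general. Item 3 itself postulates that T1-high plaque is unstable plaque. If that is right, most T1-high plaques may carry unstable CCTA features, and a high percentage would appear whether or not those features have anything to do with signal loss. At stake is the interpretation of one exploratory result: a single high percentage could be read as confirming the expectation when the association is absent or reversed.

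**Working it through.** The documents give no sample size, rate or error level for this endpoint, so there is no figure of the plan's own to reproduce. The check asks what the planned percentage can and cannot identify.

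**Notation.** Among T1-high plaques with follow-up CMR:
- N = number of plaques, and R = number that lose signal (planned);
- p = share of the R plaques that were unstable at baseline (planned);
- b = share of all N plaques that were unstable at baseline (not specified for the change analysis).

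**Identity.**
- Proportion losing signal, unstable plaques: pR / (bN).
- Proportion losing signal, other plaques: (1 − p)R / [(1 − b)N].
- Risk ratio = [p/(1 − p)] / [b/(1 − b)].

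R and N cancel. The risk ratio needs b as well as p.

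**Illustration (assumed counts).** N = 50, R = 20, and 12 of the 20 were unstable, so the planned result is 60% in every row.

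| Unstable among the 50 | Loss, unstable | Loss, other | Risk ratio |
|---|---|---|---|
| 20 (40%) | 12/20 = 60% | 8/30 = 27% | 2.25 |
| 30 (60%) | 12/30 = 40% | 8/20 = 40% | 1.00 |
| 40 (80%) | 12/40 = 30% | 8/10 = 80% | 0.375 |

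A higher planned result does not remove the ambiguity. With p = 80%, p/(1 − p) = 4, and the risk ratio is 6.0, 2.67, 1.0 or 0.44 for b = 40%, 60%, 80% or 90%.

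**Can the presence table supply b?** Only if the unstable share among baseline T1-high plaques equals the share among those followed. Complete follow-up guarantees this; incomplete follow-up need not. Take 30 unstable and 20 other plaques at baseline (b = 60%) with a true loss rate of 40% in both groups, so the true risk ratio is 1.0.
- Follow-up of 90% of unstable and 60% of other plaques gives 27 and 12 followed, of which 10.8 and 4.8 are expected to lose signal. Then p = 10.8/15.6 = 69%, and the apparent risk ratio is (10.8/4.8)/(30/20) = 1.50.
- Follow-up of 60% and 90% gives 18 and 18 followed, with 7.2 and 7.2 losing signal. Then p = 50%, and the apparent risk ratio is 1.0/1.5 = 0.67.

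**The case against.** The strongest reply is that one sentence should not be read alone. The descriptive table in the same item relates T1 presence to CCTA features and would show how many baseline T1-high plaques were unstable. With the planned count and percentage, subtraction gives the full 2×2 table. In the middle row above, 30 unstable of 50, with 12 of the 20 signal-losing plaques unstable, yields 12/30 and 8/20 at once. Item 3 also says the study will establish whether T1 signal changes across plaques, which requires classifying those that keep it, and regression for secondary endpoints is left open. Finally, the expectation is not a hypothesis with a test attached, and the aim is exploratory with an unknown number of plaques.

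Much of this stands. A reader might infer that the plan computes nothing for plaques that keep their signal, or that it cannot answer its own question. The documents do not support either reading: the data would allow the right comparison, and with complete follow-up CMR the planned outputs would contain it.

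Two things remain. The plan does not call for the derivation, and optional CMR makes complete follow-up doubtful; the last calculation above shows what unequal follow-up can do. The regression sentence is general and not tied to T1 loss. Being exploratory lowers the importance of the point, but a descriptive summary should still describe the relationship it is introduced to describe.

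**Conclusion.** The concern holds in a limited form. The stated change statistic, taken alone, does not identify the direction of the association that the plan expects: 60% fits risk ratios from 2.25 to 0.375 as the unstable share among followed T1-high plaques runs from 40% to 80%. Those shares and the plaque counts are assumptions; the algebra does not depend on them. The planned presence table fills the gap reliably only with complete 24-month CMR in baseline T1-high plaques, and no such use of it is planned.

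Severity is low. The endpoint is exploratory and descriptive. A reader might be tempted to carry the point over to the trial's main conclusion, but nothing in the documents makes the primary analysis, the sample size or the interim boundaries depend on T1 signal.

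**What to change.** In Section 6, item 3, replace the sentence giving the percentage with:

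> Among all plaques with high T1 signal at baseline and an evaluable 24-month CMR, tabulate baseline unstable CCTA features (yes/no) against loss of high T1 signal (yes/no), and report the number and proportion losing signal in each feature group and their difference; where counts allow, give a confidence interval that accounts for several plaques per participant.

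The interval is optional because T1-high plaques may be few. If so, the four counts and two proportions are enough for a descriptive aim. It would also help to report, by feature group, how many baseline T1-high plaques lacked a 24-month CMR.

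The cost is one sentence. The change needs no additional scans, participants or measurements.

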7. HUMAN SUBJECT PROTECTION

7.1. RATIONALE FOR SUBJECT SELECTION

Individuals age 40-75 (men) and 40-75 (women) from all racial/ethnical groups are eligible to participate. NIH employees who meet the eligibility requirements are eligible to be screened and considered for protocol participation. Subjects may be referred from other NIH protocols.

A comprehensive strategy of advertising and recruitment through the NIH clinical center patient recruitment and referral center will be utilized including social media and internet PSAs as well as NIH Newsletters. Walter Reed National Military Medical Center may also be a recruitment site for referring patients for participation on this protocol.

Recruitment and enrollment of NIH employee subjects will be consistent with NIH HRPP SOP 14 F.. NIH employees may voluntarily participate in this protocol. Neither participation nor refusal to participate as a subject in this protocol will have an effect, either beneficial or adverse, on the participant's employment or position at NIH. Employee subjects' privacy and confidentiality will be respected by protocol and consenting staff the same as for all subjects' participation in research protocols. However, all subjects will be made aware that there are limits to these protections. The PI, through the consenting staff members, will make the "NIH Information Sheet on Employee Research Participation" available to employees who are considering enrolling in research (SOP 14F, Appendix B). We intend to allow enrollment of staff who are affiliated or subordinate to the Principal Investigator, including technologists, nurses, scientists, students and family members. We believe we can offer them the opportunity to participate without coercion. Consent for such subjects will not be obtained from individuals in their supervisory chain of command. Instead, an associate investigator authorized in the protocol to obtain consent in this protocol and who is also a co-worker may obtain consent from a NIH employee without independent monitoring, as the IRB has waived this requirement for this protocol. Refer to the NIH Policy Manual, 2300-630-3 - Leave policy for NIH Employees Participating in NIH Medical Research Studies. See Appendix B

This age group is the most likely to benefit from an early medical intervention strategy to reduce cardiovascular events in the future.

Atherosclerosis and concomitant cardiovascular events are the leading cause of death in all major racial/ethnic subgroups in industrialized nations. Efforts to reduce the burden of cardiovascular disease are relevant to persons of all ethnicities. Our planned enrollment has been selected to be representative of the general gender and ethnic demographic subgroups of the greater Washington DC area.

Reproducibility Sub study (No longer recruiting after Amendment O Protocol dated 7/02/2020)

A subgroup of 30 participants who had CCTA defined coronary plaque will be asked to return 4 weeks after their initial CCTA scan for a second CT study using the same CCTA protocol. Additionally, the initial CCTA and reproducibility CCTA will be in accordance for total annual radiation dose exposure at the NIH as determined by the radiation safety committee. Eight to twelve patients will be selected from three groups: (a) patients with a calcium score of 0-99, (b) patients with a calcium score -100-399 and (c) patients with a calcium score of > 400. These 30 scans will be interpreted by two readers, allowing assessment of both intra and interobserver variability as well as repeatability limits.

Subjects who participate in the Reproducibility sub study will not have the cardiac MRI performed.

7.2. PARTICIPATION OF CHILDREN:

Atherosclerotic disease is not a disease of childhood and children will not be eligible for participation in this study, based on the fact they are unlikely to have this disease.

7.3. EXCLUSION OF PREGNANT WOMEN:

The risk from radiation exposure is increased in children and especially in the fetus. This can be explained by a higher rate of mitosis earlier in life (Hall 2009, Goodman and Amurao 2012). It is generally conceived that X-ray imaging should be only used in vital indications in pregnant women. In the context of this study this is not the case and therefore pregnancy is an exclusion criteria (§46.204 Code of Federal Regulations. Condition “Any risk is the least possible for achieving the objectives of the research” is not met)

7.4. EXCLUSION OF PERSONS UNABLE TO GIVE CONSENT

The research question on progression of atherosclerosis can be answered without enrolling subjects who are unable to give consent. According to NIH HRPP SOP 14E v1: 14E.6.1 A: “Ensure there is a compelling justification for including adults who cannot consent (e.g., the research question cannot be answered by enrolling only adults who can consent; participation offers the potential for important clinical benefit).” we do not plan to enroll subjects who are unable to give consent.

7.5. EVALUATION OF BENEFITS AND RISKS/DISCOMFORTS:

Phlebotomy

Associated risks include anemia and hematoma and minor pain at the puncture site.

Beta-Blockers (Atenolol and Metoprolol)

Atenolol and metoprolol are FDA approved selective β 1 receptor blocker used in treatment of several diseases of the cardiovascular system, especially hypertension, angina or myocardial infarction. The side-effects include tiredness and dizziness (10%), depression (5%), rash (5%), diarrhea (5%) shortness of breath (3%), chest pain (1%), wheezing (1%). Palpitations, congestive heart failure, peripheral edema, syncope, chest pain, dry mouth, gastric pain, constipation, flatulence, digestive tract disorders, heartburn,

hypotension, mental confusion, short-term memory loss, headache, somnolence, nightmares, and insomnia reported in very rare instances (<1%).

Calcium-channel Blockers (Diltiazem)

Diltiazem is a FDA approved cardiovascular medication for the treatment of hypertension, angina or rate control of atrial fibrillation/flutter or conversion of supraventricular tachycardia. The side-effects of chronic use include lower extremity edema (2-15%), headache (5-12%), first degree AV block (2-8%), bradycardia (2-6%), hypotension (<2%-4%), vasodilation (2-3%), extrasystoles (2%), flushing (1-2%), dizziness (3-10%), nervousness (2%), rash (1-4%), dyspepsia (1-6%), constipation (<2-4%), vomiting (2%), diarrhea (1-2%), weakness (1-4%), myalgia (2%), rhinitis (<2-10%), pharyngitis (2-6%), dyspnea (1-6%), bronchitis (1-4%), cough (<3%) and sinus congestion (1-2%).

Nitroglycerine

Nitroglycerine is a FDA approved medication for the treatment of angina pectoris due to coronary artery disease. Nitroglycerine pumpspray given to 51 chronic stable angina patients in single doses of 0.4, 0.8 and 1.6 mg as part of a study exhibited an adverse event profile that was generally mild to moderate. Adverse events occurring at a frequency greater than 2% included: headache, dizziness, and paresthesia. Less frequently reported events in this trial included (≤2%): dyspnea, pharyngitis, rhinitis, vasodilation, peripheral edema, asthenia, and abdominal pain. A notable drug interaction with phosphodiesterase inhibitors is known which can amplify the vasodilatory effects of Nitroglycerine, resulting in severe hypotension.

Statin Therapy

This study uses statin drugs for the FDA approved indications of treatment of hypercholesterolemia and atherosclerosis. The study is not designed or intended to test new indications, dosages, routes or study populations for statin drugs.

In this study a subgroup of subjects who - based on current AHA guidelines – would receive moderate intensity statin therapy (e.g. Atorvastatin 20 mg) would receive Rosuvastatin. In this context the issue of drug safety of Rosuvastatin will be addressed.

HMG CoA-Reductase inhibitors (statins) are generally well tolerated. Clinically important adverse effects of the drugs include increases in serum transaminase concentrations and myositis, with and without complicating rhabdomyolysis (Knopp 1999).

Statin induced myopathy

In 7 studies reporting rates of clinical myositis, elevation of creatinine kinase (CK) > 10 times the upper limit of normal and rhabdomyolysis, the combined incidence of these events has been less than 0.7% (Sacks, Pfeffer et al. 1996, Downs, Clearfield et al. 1998, Colhoun, Betteridge et al. 2004, LaRosa, Grundy et al. 2005, Pedersen, Faergeman et al. 2005). The highest reported rate of rhabdomyolysis was 0.53%, observed with simvastatin 80 mg daily (de Lemos, Blazing et al. 2004).

[figure not shown]
The use of high dose, intensive statin therapies to achieve very low LDL levels is a recent development. Available data, including three large randomized controlled trials (the A to Z, TNT and IDEAL studies),

indicate that high-dose statins (atorvastatin 80 mg daily, simvastatin 80 mg daily) are associated with low rates of serious musculoskeletal (<0.6%) and hepatic (<1.3%) injury (de Lemos, Blazing et al. 2004, LaRosa, Grundy et al. 2005, Pedersen, Faergeman et al. 2005) (Davidson and Robinson 2007).

We expect the population in this planned study to be similar to the JUPITER trial population in which Rosuvastatin was tested (primary prevention, age>50, no prior CVD). In the JUPITER trial (Ridker, Pradhan et al. 2012) the rate of myopathy was extremely low and not significantly different between experimental and placebo group (10 vs. 9 cases, 17802 trial participants). There was only one case of Rhabdomyolysis that occurred after closure of the trial in a 90 year old patient with pneumonia and trauma induced muscle damage. Other analyses show that Rosuvastatin compares favorably to other less potent statins when comparing the occurrence of CK elevations (see graph) (Brewer 2003).

Liver toxicity

[figure not shown]
Statin monotherapy can result in elevation of liver enzymes, most often ≤ 3 times the upper limit of normal. These elevations typically normalize without lasting injury upon discontinuation of the drug. Their clinical significance is uncertain given the extremely rare occurrence of statin related toxic hepatitis (Bays 2006, Bays, Cohen et al. 2014).

New onset diabetes

Meta-analyses of 91,140 subjects in statin trials showed a small but unexpected increase of new onset diabetes type 2 in patients treated with statins (Sattar, Preiss et al. 2010); greater age was a risk factor for new onset diabetes, but not BMI or LDL reduction. A smaller meta-analysis 3 clinical trials identified other possible risk factors for new onset diabetes in atorvastatin treated patients (Waters, Ho et al. 2011). We reflect this information on the consent form, as age and greater risk for onset of diabetes during statin

therapy.

Conclusion

Overall Rosuvastatin is a drug that has been tested in multiple large trials and has vast post marketing experience indicating a very low risk for adverse events.

Ionizing Radiation

Low dose CTA angiography and FDG PET/CT (as used in this protocol) carries a conservatively estimated lifetime additional risk of malignancy less than 0.2% in women and less than 0.1% in men, on a background lifetime risk of approximately 30% (Cronin, Marsden, & O'Doherty, 1999; Einstein, Henzlova, & Rajagopalan, 2007; Mejia et al., 1991). The primary prevention population targeted for this study is unlikely to receive significant degrees of medical radiation during the 36 months of study follow up.

Note that study participants cannot participate in all three studies (the main study, PET sub study, and reproducibility sub study) when total radiation exposure exceeds RSC limits (5.0 rem/12 months)

The following table provides radiation exposure at all required time points for participants, including optional sub-study participation:

Radiation dose estimates: Average maximum radiation exposure

Examination component	Baseline – < 12 months (rem)	12 month visit (rem)	24 month visit (rem)	36 month visit (rem)
CT: Main Study	2.134	2.134	2.134	2.134
PET sub-study	0.285*2 = 0.57 (total)	N/A	0.285	N/A

CT Reproducibility sub-study	2.134	N/A	N/A	N/A
Yearly Totals	Baseline – < 12 months (rem)	12 month visit (rem)	24 month visit (rem)	36 month visit (rem)
Total for Subjects undergoing Main CT plus PET*	2.704	2.134	2.419	2.134
Total for Subjects undergoing Main CT plus Reproducibility CT*	4.268	2.134	2.134	2.134
Total for Subjects undergoing Main CT only	2.134	2.134	2.134	2.134

*No subjects undergo both PET substudy and reproducibility substudy (No longer recruiting after Amendment O Protocol dated 7/02/2020)

Statin Use

Statins will be used for approved indications.

Iodinated contrast

The primary known risks of nonionic iodinated contrast as utilized in MDCT angiography are hypersensitivity reactions and contrast induced nephropathy. Mild to moderate adverse events such as nausea, injection site pain or urticaria occur in less than 3 percent of patients. Serious adverse events, such as hypotensive collapse, shock and death are reported in less than 1 in 10,000 patients. These reactions are generally considered idiosyncratic. Contrast induced nephropathy (CIN) is defined by an increase in creatinine more than 1 mg/dL or 50% above baseline. The risk of CIN in patients with normal renal function is considered to be negligible. The inclusion criteria for this study require baseline GFR >45 mL/min/m² as calculated by the MDRD equation to minimize risk of nephropathy. Furthermore, injection of less than 100 ccs of iodinated contrast medium is considered to present minimal risk of CIN.

